# **3. STUDY DESIGN AND SETTING**

## 3.1. Overall design

Longitudinal prospective cohort study with nested variability and case-control studies:

**Main study: Longitudinal prospective cohort study:** 610 participants will undergo assessment of candidate biomarkers (enrolment at injury day <7 days, +21 days and month 3 according to when patients are identified). Prognostic outcome assessments will follow at 6, 12 and 24 months.

**Nested study 1: Biological variability study:** biomarkers will be repeated over 12 days and 19 days in cohorts of 40 mTBI patients and 40 healthy controls.

**Nested study 2: Observational case-control prospective study:** 100 cases of mTBI will be compared to 100 healthy controls to identify novel biomarkers.

## **3.2. Study setting**

- Multi-centre recruitment and clinical assessment through the UK mTBI research network (including Defence Medical Rehabilitation Centre Stanford Hall, University Hospitals Birmingham and further centres)
- Imaging at Centre for Human Brain Health, University of Birmingham; Sir Peter Mansfield Imaging Centre, University of Nottingham; Aston Institute for Health and Neurodevelopment, and Defence Medical Rehabilitation Centre Stanford Hall

## **3.3.** Sub-studies

There will be two control cohorts in this study program:

- Healthy participants (n=20 clinical assessment day and n=20 imaging assessment day as part of the nested biological variability study)
- Healthy participants (n=100) as part of the nested case-control study

## **3.4.** Assessment of risk

All studies can be considered to involve an element of risk and in accordance with Birmingham Clinical Trials Unit (BCTU) standard operating procedures this study has been risk assessed to clarify any risks relating uniquely to this study beyond that associated with usual care. A Risk Assessment has been conducted and concluded that this study corresponds to the following categorisation: No higher than the risk of standard medical care.

## **3.5. Selection of participants**

## 3.5.1. Main Study

• Both military and civilian mTBI patients including impact, blast and sports injuries will be recruited. All consecutive potential participants will be approached to take part.

## 3.5.2. Nested study 1: Biological variability study

- Both military and civilian mTBI patients including impact, blast and sports injuries will be recruited. All consecutive potential participants will be approached to take part.
- Both military and civilian healthy controls will be recruited.

#### 3.5.3. Nested study 2: Observational case-control prospective study

- Both military and civilian mTBI patients including impact, blast and sports injuries will be recruited. All consecutive potential participants will be approached to take part.
- Both military and civilian healthy controls will be recruited.

## 3.6. Recruitment

Participants will be recruited from the study centres and their dependant patient identification centres (PICs).

Recruitment of mTBI patients will be from dedicated concussion/mTBI clinics and emergency departments.

- Birmingham University Hospitals Birmingham, Concussion service, Trauma service
- Military Defence Medical Rehabilitation Centre, mTBI team, rehab teams
- University Hospitals Coventry and Warwickshire
- Further centres

Healthy controls will be recruited from study centres, local sports clubs, etc. and online and poster advertisements (see Section 6.1).

# **4. ELIGIBILITY**

## 4.1. Main Study

## 4.1.1. Inclusion

- Age  $\geq$ 18 years &  $\leq$ 60 years
- mTBI: Acute (<3 months) mTBI (VA/DoD criteria, Table 3 below)

#### Table 3: Classification of TBI Severity

Criteria	Mild	Moderate	Severe
Structural imaging	Normal	Normal or	abnormal
Loss of Consciousness	0-30 min	>30 min and <24 hours	>24 hours
Alteration of consciousness / mental state*	up to 24 hours	>24 hours; severity b	ased on other criteria
Post-traumatic amnesia	0-1 day	>1 and <7 days	> 7 days
Glasgow Coma Scale (GCS) (best available score in first 24 hours)*	13-15	9-12	<9

(If a patient meets criteria in more than one category of severity, the higher severity level is assigned)

\*Alteration of mental status must be immediately related to the trauma to the head. Typical symptoms would be looking and feeling dazed and uncertain of what is happening, confusion, difficulty thinking clearly or responding appropriately to mental status questions and being unable to describe events immediately before or after the trauma event.

#### 4.1.2. Exclusion

- Prior diagnosis of PTSD or severe mental illness (as defined in section 23.4 Appendix 2)
- Pregnancy
- Prior brain injury (from trauma, stroke or other aetiologies) without full functional and symptomatic recovery
- Inability to comply with study schedule or follow-up\*
- Inability to provide informed consent (e.g. due to cognitive impairment)
- Any progressive neurodegenerative or neuroinflammatory condition
- Alcohol use disorder or drug dependence, in the medical opinion of the investigator
- Patients with medical conditions that are unstable or untreated

\*Note that some recruited participants may not be able to take part in the imaging aspects of the study since they may fail MRI suitability screening (e.g. metal/shrapnel from blast injury). This does not exclude them from the wider study, as they can complete all other assessments. However, all participants taking part in the imaging variability and case-control nested studies must pass the MRI screening to be eligible.

## 4.2. Nested study 1: Biological variability study

mTBI cohort eligibility as per main study in Section 4.1. The inclusion and exclusion criteria for the healthy controls (variability) is as below:

#### 4.2.1. Inclusion

• Age ≥18 years & ≤60 years

#### 4.2.2. Exclusion

- Prior diagnosis of PTSD or severe mental illness (as defined by Section 23.4 Appendix 2)
- Pregnancy
- Prior brain injury (from trauma, stroke or other aetiologies) without full functional and symptomatic recovery
- Inability to comply with study schedule or follow-up
- Inability to provide informed consent (e.g. due to cognitive impairment)
- Inability to safely enter the MRI environment (for imaging variability and case-control study)
- Any progressive neurodegenerative or neuroinflammatory condition
- Cardiovascular or cerebrovascular disease or hypertension (no current diagnosis/medication)
- Alcohol use disorder or drug dependence, in the medical opinion of the investigator
- Patients with medical conditions that are unstable or untreated
- History of pituitary hormone deficits

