Optic nerve damage caused by trauma is termed traumatic optic neuropathy. Historic data suggests that the prevalence of traumatic optic neuropathy causing severe visual loss is between 0.5 and 5% in TBI patients; more recent case series suggest that more subtle retinal and visual changes after TBI may be much more frequent, being present in many elite athletes after sports head injuries [112, 114, 115]. The OCT measures of peripapillary retinal nerve fibre layer (RNFL) thickness, macular RGC layer and choroidal thickness were both thinner in patients with mTBI than controls, demonstrating loss of RGC axons and a global reduction in blood flow respectively [116, 117]. Both global RNFL and the macular RGC nuclear layer were thicker in athletes with previous concussion than those without, suggesting long-term gliosis, and these changes were better able to distinguish these two groups than balance and reaction time performance tests.

Evidence for functional biomarkers in mTBI is seen in the pupil-light reflex. This assesses both afferent (RGC) and efferent (cranial nerve III) function and is frequently abnormal after mTBI with multiple metrics including 75% recovery time and constriction latency separating strongly between mTBI and control patients [118].

Imaging of the optic nerve head shortly after injury using cutting edge high magnification OCT has the potential to detect early structural changes such as axonal swelling after injury that is not detectable with standard imaging and analysis of optic nerve head blood flow (which is in part activity dependent), and may predict subsequent neurodegeneration [119, 120].

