## 1.10. Workstream 8, cerebral physiology

### 1.10.1. Background

Mild TBI is characterised by a period of increased cerebral vulnerability post-injury, where the brain is more sensitive to additional trauma [153]. The increased observed post-mTBI may reflect a fundamental difference between physiological recovery and clinical recovery – heavily based on medical symptom resolution, which guides return to duty and play decisions. Studies have reported alterations in physiological parameters that persist far beyond the typical 7-10 days of clinical recovery. Among other physiological markers, CBF [154], myelin content [155], and cerebral metabolites [156] have demonstrated recovery profiles in the order of 30+ days. Alterations in CBF and its regulation are thought to play an important role in the pathophysiology underlying mTBI [157]. More broadly, vascular responsiveness is an established biomarker of vascular dysfunction, with the sensitivity to detect the first signs of dysfunction [158]. Given this, targeting measures of cerebrovascular responsiveness to quantify and track mTBI severity and recovery are key.

The neurometabolic cascade identified above is known to have an impact on neurotransmission that results in an imbalance of the major excitatory (glutamate) and inhibitory (gamma-aminobutyric
acid) transmitters in the brain [158, 159]. This imbalance can be measured on a physiological level using transcranial magnetic stimulation to measure the excitatory state of the motor cortex. These measures have been shown to be sensitive to changes in acute mTBI and in PCS.

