## 1.10.1.4. Transcranial magnetic stimulation (TMS)

Following mTBI, one of the most consistently observed changes is an elongation of the TMS measure – the cortical silent period [171-174]. These changes are seen immediately following sub-concussive impacts (e.g. heading a football [175]) and continue for months to years following concussive injury [172, 176-179], and represent changes to the excitatory/inhibitory balance in the cortex.

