## 4.3. Nested study 2: Observational case-control prospective study

mTBI cohort as per main study in Section 4.1. Healthy controls as per biological variability study in Section 4.2.

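### The healthy-control exclusion sets no minimum time since a concussion, so a person recovered from an mTBI within the last 3 months meets both the case and the control criteria; the likely effect is small and the repair is one line.

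*Protocol*

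**What the plan says.** The only inclusion criterion for healthy controls is "Age ≥18 years & ≤60 years" (Protocol 4.2.1). The one exclusion that bears on head injury is "Prior brain injury (from trauma, stroke or other aetiologies) without full functional and symptomatic recovery" (4.2.2). It turns on recovery alone and gives no time since injury. Section 4.3 carries these criteria into nested study 2: "Healthy controls as per biological variability study in Section 4.2".

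Cases enter under "mTBI: Acute (<3 months) mTBI (VA/DoD criteria, Table 3 below" (4.1.1). Ongoing symptoms are not required, and the case exclusion for earlier brain injury (4.1.2) has the same wording as the control exclusion.

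The background describes changes that symptoms do not track. Section 1.10.1 reports "alterations in physiological parameters that persist far beyond the typical 7-10 days of clinical recovery" and puts recovery of cerebral blood flow, myelin content and cerebral metabolites in the order of 30 days or more. Section 1.10.1.4 says that changes in the TMS cortical silent period "continue for months to years following concussive injury". The silent period is a primary biomarker in Table 2.

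On sources of controls, section 3.6 states: "Healthy controls will be recruited from study centres, local sports clubs, etc. and online and poster advertisements". Section 5.2 adds websites and social media related to head injury, sport and military personnel.

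**The concern.** The two groups of the case-control study are not mutually exclusive on the written criteria. Recent mTBI is the exposure that defines a case. A control with a recent, recovered mTBI is therefore misclassified, which is a different problem from confounding.

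The control rule certifies health by function and symptoms, while the background says that some of the measured physiology recovers later. If a control still carries part of the injury effect on a marker, the estimated case-control difference for that marker moves toward zero.

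The same criteria govern the healthy reference in the biological variability study. Both nested studies supply information to the Delphi reduction of candidate biomarkers (14.3), and section 1.13 says that markers with excess variability may be dropped. What is at stake is a modest understatement of slower-recovering markers at the screening stage.

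**Working it through.** **Step 1: do the criteria overlap?** Take a person aged 18 to 60, concussed six weeks ago, fully recovered, with none of the other exclusions.

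| Rule | As a case | As a healthy control |
|---|---|---|
| Age | met (4.1.1) | met (4.2.1) |
| mTBI in the last 3 months | required, met (4.1.1) | not mentioned |
| Earlier brain injury without recovery | none, passes (4.1.2) | recovered, passes (4.2.2) |

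Both sets of criteria are satisfied. A person who still has symptoms cannot be a control, so the overlap is confined to recovered recent injuries.

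**Step 2: reproduce the plan's figure.** Inputs from section 14.2: 100 per group, difference 1.5, SD 3. The section states no significance level; two-sided 5% is assumed.

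- Standard error = 3 × √(2/100) = 0.4243
- Noncentrality = 1.5 / 0.4243 = 3.536
- Power (two-sample t test, 198 degrees of freedom) = 94.0%

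This agrees with the stated power of more than 90%.

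**Step 3: dilute the contrast.** Let c be the share of controls recently injured and f the fraction of the case effect they still carry. Both are assumptions. The detectable difference is 1.5 × (1 − c·f). The table uses f = 1, the worst case.

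| c | Difference | Power |
|---|---|---|
| 0% | 1.500 | 94.0% |
| 0.15% | 1.498 | 94.0% |
| 1% | 1.485 | 93.6% |
| 1.5% | 1.478 | 93.4% |
| 3% | 1.455 | 92.7% |
| 5% | 1.425 | 91.7% |
| 10% | 1.350 | 88.6% |

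Power reaches 90% at c of about 8%. With f = 0.5, a share of 10% gives the same difference as the 5% row (1.425) and the same 91.7%.

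**Step 4: what share is plausible?** Section 1.1 puts the mTBI rate above 600 per 100,000. Reading it as annual is an assumption.

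- Per 3 months: 0.6% × 3/12 = 0.15%
- Expected among 100 controls: 0.15 people; among 20 variability controls: 0.03 people
- Tenfold enrichment: 1.5%; twentyfold: 3%
- Enrichment needed to reach 8%: 8 / 0.15 = about 53-fold

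The published rate is a floor and sports-club volunteers will be enriched, so 1% to 3% is used as the working range. The protocol gives no figure for recent concussion among such volunteers.

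**The case against.** The strongest objection is size. On the protocol's own incidence figure hardly any controls would be recently injured, and even a twentyfold enrichment leaves power near 93%. That stands, and it is why the point is minor. The main study of 610 patients uses no controls, so the primary outcome is not directly touched. That also stands.

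A second objection is that existing provisions cover the gap. TBI history is taken at the structured interview (8.2.1), and the regressions adjust for known clinical confounders as appropriate (14.2). This stands only in part. The interview excludes nobody, and covariate adjustment is not a substitute for keeping people who meet the case definition out of the control group. The interview is tied to a first clinical assessment visit, whereas variability controls may be booked directly to the imaging visit (5.4.3). The word healthy may prompt some sites to screen informally, but no criterion requires it.

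A reader might infer several stronger things that the protocol does not support:

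- **A large loss of power from past TBI.** Section 1.1 says 32% of people have a TBI before age 25. That is lifetime history of any severity. Cases share it under the identical rule in 4.1.2, so it does not bound the dilution.
- **A weaker retinal contrast.** Section 1.7.1 reports thinner RNFL in mTBI patients than in controls, but layers "thicker in athletes with previous concussion than those without, suggesting long-term gliosis". On those statements, previously concussed controls could widen the RNFL contrast.
- **Changes in all markers outlasting symptoms by months to years.** That period counts from injury and concerns the silent period only. For blood flow, myelin and metabolites the text says 30 days or more.
- **Cerebrovascular reactivity among the slowest markers to recover.** Section 1.10.1 gives no recovery time for it.

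**Conclusion.** The textual gap is certain: sections 4.1.1 and 4.2.2 allow one recovered person to meet both definitions, and the background gives reason to think that such a control is not a clean reference for blood flow, myelin, metabolites or the silent period. For those markers the expected direction is dilution.

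The size is small. The estimate rests on the 14.2 continuous example, a two-sided 5% test, a recently injured share of 1% to 3% and full carry-over of the case effect. On those assumptions power loses about 0.4 to 1.3 percentage points and stays above the stated 90%. Any harm to the variability study is possible but not quantified. Severity: minor.

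**What to change.** Add one exclusion to section 4.2.2, applying to healthy controls in both nested studies: no TBI or concussion within the 3 months before enrolment. This is the study's own case window and makes the groups mutually exclusive. Ask the question at screening, so that imaging-variability controls are covered as well.

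For controls already enrolled, check injury history, contacting those with no recorded clinical history. Run a sensitivity analysis without any found to have been injured in that window.

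A longer washout, such as 12 months, is not needed: it would bar controls for a recovered injury that cases are still allowed to have. Adjustment for earlier lifetime TBI can be left to the SAP.

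The cost is one eligibility line, one screening question and a few volunteers turned away.

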## 4.3. Nested study 2: Observational case-control prospective study

mTBI cohort as per main study in Section 4.1. Healthy controls as per biological variability study in Section 4.2.

## 4.4. Co-enrolment

Co-enrolment in other observational studies as well as in interventional trials is permitted.

# **5. IDENTIFICATION OF PARTICIPANTS**

## **5.1. Identification of mTBI patients**

Potentially eligible participants will be identified by their clinical care teams in secondary care NHS Trusts including emergency departments as well at MoD treatment facilities.

NHS and military research staff may assist clinicians with screening and use of electronic record searches to help identify patients according to local permissions as appropriate.

Once potential participants are identified according to the inclusion and exclusion criteria, they will initially be approached by a member of the clinical care team (including embedded researchers where appropriate) to see if they would be happy to discuss potential participation in research. If they agree to discuss the study, a member of the research team will then introduce it, and the informed consent process will take place using the online consent form in person or remotely by telephone or video call as appropriate as per section 6.

## 5.1.1. Participant Identification Centres

At some sites, participants will also be recruited via PICs, and referred to the main recruiting centre. For example, potentially eligible military participants may be identified in military primary care, and rehabilitation services.

## 5.1.2. Social media by way of patient forums, Facebook, Twitter, etc.

The study will be advertised for the purposes of recruitment using ethically approved material via websites and social media platforms related to head injury, sport and military personnel. Posters in clinical areas and advertisements on charity websites will also be developed for promoting and supporting the study for recruitment.

## 5.2. Identification of healthy controls

The study will be advertised for the purposes of recruiting healthy controls using ethically approved material via research facilities, websites and social media platforms related to head injury, sport and military personnel and contact details for the research team will be provided to make first contact regarding the study. Once contact is made, the informed consent process can take place as per section 6.

## 5.3. Screening

Details of all people approached about the study will be recorded on the mTBI-Predict Participant Screening Log, which will be kept in the Investigator Site File and should be available to be sent to the Study Office upon request.

## 5.4. Study entry points

## 5.4.1. mTBI patients

mTBI patients may enter the study at any time up until 3 months after their injury, and will have their first assessment at the next timepoint after their injury:

- Within 7 days of the injury. After consenting, visit 1 procedures should be completed (section 7.5).
- 21 days (± 7 days) post-injury. After consenting, visit 3 should be booked.
- 3 months (± 7 days) post-injury After consenting, visit 8 should be booked.

## 5.4.2. Healthy controls for case-control study

Once healthy controls have given informed consent, a research team member will explain how to use the app and actigraphy equipment, which will be used at home prior to visit 2, and visit 3 should be booked.

## 5.4.3. Healthy controls for variability study

Once healthy variability controls have given informed consent, a first visit 3 or 4 should be booked.

# 6. CONSENT AND REGISTRATION

It is the responsibility of the Principal Investigator (PI) to obtain informed consent for each participant prior to performing any study related procedures. This task can be delegated by the PI to other members of the local research team if local practice allows and this responsibility has been documented in the site delegation log.

Obtaining consent can be undertaken in-person or remotely and will use electronic online consent forms. If electronic consent is unavailable, consent can be done over telephone, or on paper. Copies of the PIS and ICF will also be available from the Study Office and will be printed or photocopied onto the headed paper of the local NHS Trust.

If the patient is lacking capacity on initial approach, they will ordinarily be admitted for observation in hospital. For mTBI, capacity should be regained within 24 hours and the research nurse can reapproach the patient for consent.

A Participant Information Sheet (PIS) (appropriate to the study arm that they are being recruited to) will be provided to facilitate the consent process. The PI or delegate will explain the aim of the study, the study procedures, and the anticipated benefits and potential hazards of taking part. They will explain that participation is voluntary and that the participant is free to decide not to take part and may withdraw from the study at any time without this affecting their standard of care. The potential participant will be given sufficient time and opportunity to read the PIS, ask questions, and discuss their participation with others outside of the site research team if required.

If the potential participant then wishes to participate in the study, they will be asked to electronically sign and date the latest version of the Informed Consent Form (ICF). The PI or delegate will then electronically countersign and date the ICF. For telephone consent, a PDF copy of the blank ICF will be emailed to the participant by the Research nurse. The participant will sign the ICF and email back to the nurse who will add their signature.

All potential participants will be approached to also take part in the biological variability study until the required sample size is reached; all potential participants will then be approached to also take part in the case-control study until the required sample size is reached.

A copy of the signed ICF will be emailed to the participant. Photocopies of the signed ICF will be available if consent was obtained via paper. Participants will consent to their email address being stored and used for this purpose (they will also consent to their email and/or mobile number being used for data collection app reminders). Should participants wish to do so, they can receive a printed

copy of the ICF instead. A copy will be stored in the medical notes and a copy in the Investigator Site File. Once the participant is entered into the study, the participant's study number will be entered on the ICF maintained in the Investigator Site File.

In addition, the participant will understand and acknowledge that a copy of the signed ICF will be transferred electronically to the study team at BCTU for review and storage in the study database.

Details of the informed consent discussions will be recorded in the participant's medical notes. This will include date of discussion, the name of the trial, summary of discussion, version number of the PIS given to participant, version number of ICF signed and date consent received. Where consent is obtained on the same day that study related assessments start, a note should be made in the medical notes of what time consent was obtained and what time procedures started.

At each visit the participant's willingness to continue in the study will be ascertained and documented in the medical notes. Throughout the study the participant will have the opportunity to ask questions about the study. Any new information that may be relevant to the participant's continued participation will be provided. Where new information becomes available which may affect the participants' decision to continue, participants will be given time to consider and if happy to continue they will be re-consented. Re-consent will be documented in the medical notes. The participant's right to withdraw will remain.

Participants will be asked to give consent to allow members of the local research team to access their primary care medical records to gain a complete and detailed medical history at baseline.

Visits throughout the informed consent process and beyond will take place in person at the clinic or participant's home, or by telephone or video call as per local practice where patient and/or public health circumstances dictate. Where visits are in the participant's home, or by telephone or video call, due care will be paid to ensure the participant is in a suitably safe and confidential environment before proceeding.

